6.8.3 Analysis plan

For each woman, we will determine the estimated GA based on the initial first trimester visit, which will be our reference value. Then, for each approach, we will calculate the estimated GA and the difference between this estimate and the reference value. In a primary analysis, we will compare the mean absolute errors for the different approaches. The approach with smaller mean absolute error is preferred. In secondary analyses, we will compare the root mean squared errors for the different approaches.

Because approaches are conducted on all women, comparisons of approaches are naturally controlled for all possible time fixed confounding factors. To account for differential loss to follow up, if loss to follow up exceeds 9%, and possible resultant selection bias, we will employ inverse probability of censoring weights.³ Censoring weights will be estimated using a pooled logistic regression model fit by maximum likelihood.⁴ Continuous covariates will be included using restricted quadratic splines.⁵

6.9 Dissemination of findings

Study findings will be disseminated through appropriate local channels, including academic and public health research symposia. One or more publications will also be submitted to a peer-reviewed journal. The study participants' privacy and confidentiality will be strictly maintained in all results dissemination or publication activities.

Sharing of data generated by this project is an essential part of our proposed activities and will be carried out in several different ways. The findings of this study will be made available through appropriate local channels, including academic and public health research symposia. We will make results available to the community of scientists interested in maternal and child health to avoid unintentional duplication of research.

Presentations at national scientific meetings. It is expected that several national meeting audiences would be interested in the findings generated by proposal completion. We plan to present findings at the annual meeting of the Society for Maternal Fetal Medicine, the annual meeting of Pediatric Academic Societies, and the International Conference on Maternal and Child Healthcare.

Access to data. This research will enroll 400 participants, each of whom will attend 3 follow-up visits in pregnancy (i.e., up to 1,200 research ultrasound scans performed). In addition to ultrasound data, the final study dataset will include a limited amount of demographic and behavioral data, medical history, pregnancy outcome, and physical exam findings. We will make de-identified data and associated documentation available to users only under a data-sharing agreement that binds the user to: (1) using the data for research purposes; (2) securing the data with appropriate technology; (3) destroying or returning the data after analyses are completed; (4) making appropriate attribution to data provenance; and (5) ensuring the Gates Foundation Global Access requirements are met.

7.0 Ethical Considerations

The protocol, informed consent documents, and any subsequent modifications will be reviewed and approved by all relevant ethics committees responsible for oversight of the study and maintaining Federal Wide Assurances (FWA) with the Office for Human Research Protections (OHRP) approval. For this study, relevant ethics committees include the

University of Zambia Biomedical Research Ethics Committee and the University of North Carolina at Chapel Hill Institutional Review Board.

Participation in this study will be voluntary. All participants involved in prospective collection of research data will provide written, informed consent prior to study enrolment. All care and procedures will be conducted according to local standards of routine clinical care. All staff who have contact with participants will receive training on the protection of human research participants prior to conducting any study activities and routinely thereafter. Key staff will also complete Good Clinical Practices training.

7.1 Informed consent

Discussions with prospective participants and informed consent procedures will be conducted in private to protect patient confidentiality. Where possible, a private room will be used to discuss the study and potential participant's eligibility. If a private room is not available, a designated area far enough away from other participants such that they cannot hear the conversation will be used. Study staff will obtain written informed consent from all participants. The study procedures, risks, and benefits will be discussed, and the responsible staff member will answer all questions prior to obtaining consent. The consent forms will be translated into local languages and back-translated into English to ensure accurate translation. All versions of the consent forms will be approved by the relevant ethics committees prior to study initiation. For illiterate participants, a literate impartial witness will be present during the entire consent process to ensure that all of the relevant information has been provided and the participant voluntarily gives consent.

Eligible women who do not wish to participate in this study will continue to receive antenatal care and treatment according to local clinical standards.

7.2 Potential risks to participants

Investigators will make efforts to minimize risks to participants. This study involves minimal risk to participants, no greater than at routine antenatal or clinical examinations. Participants will be asked to have additional ultrasound procedures beyond what they would normally receive for clinical purposes, but because ultrasound uses sound waves instead of radiation, we do not expect this additional exposure to offer any significant risk. Providers have used ultrasound for more than 30 years, and they have not found any dangerous risks.

Physical risks also include the risk of discomfort, bruising or swelling from venipuncture. The risks that are associated with venipuncture are infrequent and minimized with the use of proper technique. Such risks include (1) bleeding, (2) bruising, or (3) rarely infection at the site of needle insertion. Individuals may also rarely become faint, in which case symptoms abate after several minutes in a recumbent position. Blood volumes for the study have been calculated to ensure safety and participants will be reassured that such feelings are transient.

Participation in clinical research includes the risks of loss of confidentiality and discomfort with the personal nature of questions, particularly when discussing HIV infection or sexual behaviors. At each step in the study, we will protect participant privacy and confidentiality to reduce these risks (e.g., consenting participants in a private setting, not including names on case report forms, etc.). Although investigators make every effort to protect participant privacy and confidentiality, it is possible that participant involvement in the study could become known to others, and that social harms may result.

The confidentiality of all study records will be safeguarded to the extent legally possible. To maintain participant confidentiality, all laboratory specimens, reports, study data and administrative forms will be identified by a coded number only. All databases will be secured with password-protected access systems, and computer entries will be identified by coded number only. Forms, lists, logbooks, appointment books, and any other listings or data forms that link participant ID numbers to other identifying information will be stored in a separate, locked cabinet. All data analysis will be performed using datasets which have only the study number as a unique identifier. Clinical information with individual identifiers will not be released without the written permission of the participant. We expect these procedures to adequately protect participant confidentiality.

7.3 Potential benefits to participants and others

Individual participants may benefit from clinical monitoring through routine ultrasounds and health assessments, with referrals provided as needed. They may also receive no direct benefit. Women may appreciate the opportunity to see their fetus during pregnancy and will be provided with printed or electronic copies of ultrasound images.

Knowledge generated from this study has the potential to contribute to the development of widely deployable ultrasound technologies that can assess gestational age and other important obstetric conditions while requiring minimal user expertise, which has the potential to improve maternal and infant outcomes in low-resource settings worldwide.

In summary, risks to participants in this study are minimal and do not differ significantly from the risks inherent in the local standard of care for pregnant women. These risks are reasonable in relation to the anticipated benefits of the project.

7.4 Inclusion of children, sub-populations, and vulnerable populations

This study focuses specifically on pregnant women and, as such, they must be included in our study population. Prisoners will be excluded as they receive care at separate facilities.

8.0 Timeline

We have allocated 3 months to start-up activities and 21 months to study implementation.

Month	Q1	Q2	Q3	Q4	Q5	Q6	Q7	Q8
Protocol and CRF development	■							
Ethical submission and review	■							
Site preparation	■							
Site training	■							
Enrollment		■	■	■	■			
Data entry and management		■	■	■	■			
Follow-up		■	■	■	■	■		
Statistical analysis						■	■	■
Publication and dissemination								■

9.0 Budget – Zambia field costs

The following costs are projected over the two-year study period.

ITEM	ZMW TOTAL	USD TOTAL
Personnel	3,750,000	\$250,000
Equipment	750,000	\$50,000

Supplies & materials	457,500	\$30,500
Participant reimbursement	180,000	\$12,000
Other – communication, data, translation, regulatory, community outreach, shipping, and training costs	937,500	\$62,500
TOTAL	6,075,000	\$405,000

Diagnostic Accuracy of a Novel Machine Learning Algorithm to Estimate Gestational Age

Analysis Plan

Version 1.1

08 June 2022

Funded by:

The Bill and Melinda Gates Foundation
OPP 1191684

Principal Investigators:

[name], MPH
[name], MMed, MSc

Study Registration:

ClinicalTrials.gov
NCT05433519

For each pregnancy, the gestational age (GA) estimated at the first ultrasound establishes the estimated due date (EDD) and is used to define the “ground truth” gestational age for all visits that follow. Then, during study visits 1, 2, and 3, we will assess the diagnostic accuracy of both the index test (i.e., the FAMLI AI algorithm interpreting blind sweep data) and the clinical reference standard (i.e., standard fetal biometry performed by a trained sonographer). Accuracy will be estimated for both the index test and the clinical standard at each visit by comparing the test’s gestational age estimate to the previously determined ground truth gestational age.

The Diagnostic Accuracy (DXA) Study primary outcome is the mean difference in absolute errors in gestational age assessment for the index test versus the clinical reference standard (expert biometry) conducted in the primary evaluation window (visit 1), defined in the protocol as between 14 $\frac{0}{7}$ and 27 $\frac{6}{7}$ gestational weeks, inclusive. The absolute errors, in days, for the index test and expert biometry are measured with respect to the gold standard assessment taken prior to 14 weeks of gestation. We will estimate a Wald-type 95% confidence interval for this difference. Specifically, let m be the mean of the difference in absolute errors for each participant (i.e., $m = n^{-1} \sum_{i=1}^n |y_{1(i)}| - |y_{2(i)}|$, where $y_{j(i)}$ is the error, in days from gold standard, for method j and participant i), and σ be the standard error of m , then the 95% confidence interval is given by $m \pm 1.96\sigma$. A negative or positive mean difference whose 95% confidence interval does not include zero indicates the index test is superior or inferior to expert biometry, respectively. A difference whose 95% confidence interval is contained in the prespecified equivalence range of -2 to 2 days indicates the index test is equivalent to expert biometry. To establish equivalence, two one-sided statistical tests on the difference between the mean absolute error of the index test (μ_t) and the mean absolute error the clinical reference standard (μ_r) will be carried out based on a predefined margin $c = 2$ days i.e. $H_{01}: \mu_t - \mu_r \leq -c$ and $H_{02}: \mu_t - \mu_r \geq c$.¹

To ensure fair comparison, the analysis will be restricted to only those cases where both the index test and clinical reference standard (expert biometry) are available; hence, we have paired estimates of the two methods. This means that for the primary study outcome, the difference in the MAEs of the two approaches corresponds to the mean of the pairwise difference in absolute errors, m . Study visits that are missing a gestational age estimate from either the index test or the clinical reference standard will be excluded. Potential reasons for missingness include when the index test model indicates a failure to calculate GA based on the blind sweeps of that study, patient non-attendance of a scheduled study visit, and data loss. By design, participants who experience a pregnancy loss after screening but before visit 1 will be excluded from the DXA Study (and therefore from analysis) and replaced with other participants to be enrolled.

As secondary analysis, we will present the difference in root mean squared error and Wald-type 95% confidence interval. Also, as secondary analysis, we will plot the empirical cumulative distribution function for the absolute error produced by the index test and expert biometry. We will present the difference in proportions with absolute error below 7 and 14 days between the index test and expert biometry, along with Wald-type 95% confidence intervals. The primary analysis compares the index test to the clinical reference standard in the pre-defined primary evaluation window (Figure 1). In secondary analyses we will make the same comparison in two

secondary windows, defined (a) between 28⁰/₇ and 36⁶/₇ weeks of gestation, inclusive (visit 2) and (b) between 37⁰/₇ weeks and 40⁶/₇ weeks, inclusive (visit 3).

Figure 1: Gestational age definitions of the primary and secondary evaluation windows

GA	Enroll													Primary Evaluation Window										Secondary Evaluation Windows																														
	1	2	3	4	5	6	7	8	9	10	11	12	13	14	15	16	17	18	19	20	21	22	23	24	25	26	27	28	29	30	31	32	33	34	35	36	37	38	39	40														
<12 ⁰													14 ⁰ to 27 ⁶														28 ⁰ to 36 ⁶														37 ⁰ to 40 ⁶													

While the primary analysis will compare the index test interpreting blind sweep data as generated by an untrained (novice) sonographer to expert biometry overall, we will also compare the model performance when the blind ultrasound sweeps are generated by an expert sonographer. As in our primary analyses, these analyses will assess model error and clinical reference standard error by comparing estimates to previously established ground truth. Additional secondary analyses will include comparisons in prespecified subsets defined by geography (i.e., Zambia vs North Carolina), medical and obstetrical risk factors (maternal obesity, hypertension, diabetes, fetal growth restriction, oligohydramnios, and polyhydramnios).

Because both the index and reference standard tests are conducted on all women, comparisons of approaches are naturally controlled for all possible time-fixed confounding factors. To account for differential loss to follow-up, if loss to follow-up exceeds 9% and selection bias is suspected, we will employ inverse probability of censoring weights. Censoring weights will be estimated using a pooled logistic regression model fit by maximum likelihood.² We will specify *a priori* a set of possible common causes including demographics, medical, and obstetrical factors, for inclusion as covariates in the model. A list of possible covariates is shown below in Table 1. Continuous covariates will be included using restricted quadratic splines.³

Table 1: Possible covariates for inverse probability of censoring weights modeling

Age, years	BMI, kg/m ²	Estimated gestational age at enrollment, weeks
Education, years	HIV serostatus*	
Marital/partner status	Syphilis serostatus	Transvaginal cervical length, cm
Gravidity (total pregnancies)	Hemoglobin, mg/dL	Study site
Parity (prior deliveries)	Bacteriuria	
Prior miscarriage	Alcohol use in pregnancy	
Prior stillbirth	Tobacco use in pregnancy	
Prior preterm birth	Illicit drug use in pregnancy	

*We will also consider inclusion of HIV-specific covariates through interaction terms (e.g., timing of HIV diagnosis and antiretroviral therapy initiation, antiretroviral therapy regimen, viral load, CD4 count)

References

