Figure 9 shows the statistical power for superiority as a function of the difference in absolute error between approaches (in days) and sample size. At the null hypothesis of 0 difference, the statistical power is approximately 5%, regardless of sample size (i.e., this is a valid statistical test). At a -0.5-day difference in absolute error (i.e., the FAMLI Technology estimated GA reduces random error by 1/2 day over standard approach), a sample size of 200 has less than 60% power, while a sample size of 400 has 80% power. Figure 10 shows the expected 95% CI as a function of the difference in absolute error between approaches (in days) and sample size.

In conclusion, we settle on a sample size of 400 women for the FAMLI study. Select numeric results are also shown in Table 4.

Table 4: Statistical power for non-inferiority and superiority, by difference in absolute error, and sample size *

T	Days	Statistical Power, %					
		Non-inferiority			Superiority		
		N=200	N=300	N=400	N=200	N=300	N=400
1.00	-2.22	0	0	0	100	100	100
1.25	-2.06	2	1	1	100	100	100
1.50	-1.89	9	10	12	100	100	100
1.75	-1.72	28	40	49	100	100	100
2.00	-1.53	60	75	86	100	100	100
2.25	-1.35	83	94	98	100	100	100
2.50	-1.16	95	99	100	100	100	100
2.75	-0.97	99	100	100	99	100	100
3.00	-0.77	100	100	100	89	98	100
3.25	-0.58	100	100	100	66	83	92
3.50	-0.38	100	100	100	34	47	59
3.75	-0.20	100	100	100	12	15	18
4.00	0.00	100	100	100	6	5	6
4.25	0.19	100	100	100	11	13	16
4.50	0.38	100	100	100	28	39	50
4.75	0.59	100	100	100	53	68	80
5.00	0.78	98	100	100	74	89	95
5.25	0.98	91	98	100	89	97	99
5.50	1.18	72	87	94	96	99	100
5.75	1.38	46	64	75	98	100	100
6.00	1.58	26	33	42	100	100	100

* Monte Carlo simulation error < 2%

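### The Wald interval for the 14-day difference can collapse to zero width if errors are as small as the planning model implies, and the SAP sets no small-sample method for its subsets

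*SAP*

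**What the plan says.** The SAP restricts the analysis to visits with both estimates: "hence, we have paired estimates of the two methods". For the primary outcome, the mean difference in absolute error, it states: "We will estimate a Wald-type 95% confidence interval for this difference". The formula given is the mean plus or minus 1.96 standard errors.

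Among the secondary analyses, the SAP will report the "difference in proportions with absolute error below 7 and 14 days between the index test and expert biometry, along with Wald-type 95% confidence intervals". It then extends the analysis to the later visits: "In secondary analyses we will make the same comparison in two" further windows. No exact, score or adjusted interval is offered for the case of few or no disagreements.

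On subsets it says: "Additional secondary analyses will include comparisons in prespecified subsets defined by geography (i.e., Zambia vs North Carolina), medical and obstetrical risk factors", and lists obesity, hypertension, diabetes, growth restriction and the two amniotic fluid disorders. It names no interval, expected count or minimum size for them.

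On size, protocol section 6.8.2 concludes: "we settle on a sample size of 400 women for the FAMLI study". The protocol introduction expects roughly half from each country.

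**The concern.** A paired Wald interval for a difference in proportions takes its width only from the women whom the two methods classify differently. When nearly every estimate by both methods falls within 14 days, there may be no such woman. The interval then shrinks to the single value 0.

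In a study built around equivalence, a printed result of 0 (0 to 0) invites the reading that the two methods have been shown to be identical at 14 days. What the data would show is only that no disagreement happened to occur. The same mechanism acts more strongly in a subset of a few women, where 1.96 is also too small a multiplier for a mean difference. The proportion within 7 days is a named secondary outcome in protocol section 6.8.1; the 14-day cut appears only in the SAP. Nothing here reaches the primary comparison.

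**Working it through.** **Reproducing the plan's figure.** The documents give no precision figure for the proportions or the subsets. The nearest figure is Table 4 of the protocol at tau = 4 (no difference): 100% non-inferiority power for 200, 300 and 400 women, and 6, 5 and 6% superiority rejection. Simulating the section 6.8.2 model (enrollment GA 74.5 ± 10.5 days; estimate = −7 + 1.1 × enrollment GA, residual SD 4) with mean ± 1.96 SE gives 100% at all three sizes and 4.6, 5.3 and 5.4%. The model as read here matches that row.

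**14-day difference under the planning model.**
- Error = −7 + 0.1 × GA + residual. Its mean is −7 + 7.45 = 0.45 days and its SD is √(1.05² + 4²) = 4.14 days.
- Normal tail beyond 14 days: about 0.08%. With no mean bias and SD 4.13 it is 0.07%.
- Discordant pairs, about 2p(1 − p): about 0.15% (0.14% in the simpler version).
- Paired Wald SE = √{[(b + c)/n − d²]/n}, where b and c are the two discordant counts and d = (b − c)/n. If b = c = 0, the SE is 0.
- Chance of no discordant pair, (1 − D)^n: with D = 0.001525 it is 54% at n = 400 and 74% at n = 200; with D = 0.0014 it is 57% and 76%.
- Tango's paired score interval with no discordant pair is ± z²/(n + z²). At n = 400 this is 3.84/403.84 = ±0.95 percentage points; at n = 40 it is 3.84/43.84 = ±8.8 points.

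**14-day difference at the pilot rate.** Protocol section 4.1.1 gives 94.8% within 14 days for the model and no figure for biometry. I assumed 92.8 to 94.8% for biometry and independent errors, which puts discordance at 9.9 to 11.7%. By exact enumeration, Wald coverage is 94.6 to 95.1% at n = 200 to 400, with essentially no chance of zero width.

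**Subset sizes.** Applying protocol Table 1 to 400 women with no missing visits gives polyhydramnios 0.01 × 400 = 4, growth restriction 0.10 × 400 = 40 and oligohydramnios 0.11 × 400 = 44. With an expected 4, there is a 9% chance of 1 woman or none. The documents give no figure for obesity, hypertension or diabetes.

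**Behaviour in those subsets, if Wald is carried over.**

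| Quantity | n | Result |
|---|---|---|
| MAE difference, ±1.96 SE | 4 | covers about 86%; t multiplier 3.18 gives about 96% |
| MAE difference, ±1.96 SE | 8 | covers about 91%; t gives about 95% |
| MAE difference, ±1.96 SE | 40–44 | covers about 94.3% |
| 14-day difference, zero width | 4 | 61 to 84% of trials |
| 14-day difference, coverage, independent errors | 40–44 | 92 to 95% |

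The 61 to 84% range comes from (1 − D)^4. D = 0.117 (94.8 vs 92.8%, independent) gives 61%. D = 0.068 (same rates, fewer disagreements) gives 75%. D = 0.043 gives 84%; this uses normal errors with SD 6.1, from the pilot MAE of 4.9 × √(π/2), so that 2.2% lie beyond 14 days. If the methods' errors are correlated so that D is 0.068, coverage at n = 40 to 44 is 88 to 91%.

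**7-day difference.** At 71.9% (pilot) against an assumed 69%, Wald coverage is 94.8 to 94.9% at n = 200 to 400, 94.0% at n = 40 to 44 and 76% at n = 4.

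**The case against.** The strongest reply is that the pilot is better evidence than the planning model. In 249 exams, 5.2%, or about 13, fell beyond 14 days; SD 4.13 predicts 249 × 0.0007 = 0.17. If the trial resembles the pilot, the full-cohort interval will not collapse. This stands, with the caveat that the pilot figure is an overall one and its gestational-age range is not given. The SAP cannot know beforehand which error level the second-trimester window will show.

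Second, in the collapse case both methods have the same error, the true difference is 0, and an interval of 0 to 0 contains it (exact coverage 99.97%). This also stands. A reader might infer that Wald generally under-covers here. Coverage as low as 92% (SD 4.13 vs 5.5, n = 400) or 83% (SD 6.1 vs 7.0, n = 40) can be produced, but only by assuming unequal SDs that the documents do not give.

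Third, the empirical distribution of absolute error and the MAE and RMSE differences will be reported alongside, so a careful reader would not be misled. That softens the consequence but does not correct the interval.

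Fourth, protocol section 4.0 says biometry error grows with gestational age, so visits 2 and 3 should lie further from 100%. That is fair: the collapse is mainly a visit 1 risk.

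Finally, with 4 women no interval is informative. This is correct, and it argues for a minimum-size rule.

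**Conclusion.** The point holds as a minor one about secondary analyses. The SAP prescribes an interval for the 14-day difference that, on the sponsor's own planning model, would more likely than not have zero width at n = 400 (about 54 to 57%), and in about 75% of trials within one country. This rests on normal residuals, equal residual SD for the two methods and independent residuals. At the pilot rate, with biometry's rate assumed, Wald is adequate at n = 200 to 400.

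Several wider readings are tempting but not supported. The SAP does not explicitly prescribe Wald for the subsets; it is only the sole interval on offer. The documents' figures make only polyhydramnios very small. No material failure is shown for the 7-day proportion outside very small subsets. The primary MAE conclusion is unaffected: at n = 400 the t multiplier is 1.966 against 1.96.

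**What to change.** Amend the SAP before analysis in three places.

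1. Replace the Wald interval for the 14-day difference with a paired score interval, either Tango's or Newcombe's paired hybrid-score. Use the same method for the 7-day difference for consistency, although Wald is adequate there except in very small subsets.
2. State the interval for MAE differences in subsets, using the t quantile with n − 1 degrees of freedom in place of 1.96.
3. Report subsets below about 10 women descriptively, without an interval.

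The cost is a few lines of SAP text and a different software call. The proportion intervals become slightly wider and asymmetric. Sample size, data collection and the primary analysis stay as they are.
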